13.1.3. Statistical Methods for Pharmacokinetic Parameters

PK parameters will be summarized by INP103 dose group using descriptive statistics (number of non-missing observations, arithmetic mean, SD, median, minimum, maximum, geometric mean, coefficient of variation as a percent (CV%) and geometric CV%).

Additional analyses will be performed as deemed necessary upon review of the data.

13.1.4. Dose Proportionality

Dose proportionality will be evaluated for baseline corrected C_{max} and AUC_{0-2h} . Dose proportionality will be assessed using the power model with log-transformed PK parameter values and log-transformed dose. The power model will be used to estimate the slope parameter and the 90% confidence intervals for the slope.

The general form of the power model is described as:

$$\ln(\text{PK Parameter}) = \beta_0 + \beta_1 \ln(\text{Dose}) + \varepsilon$$

This approach is usually referred to as a power model because after exponentiation:

$$\text{PK Parameter} = \alpha \text{Dose}^{\beta_1}$$

where α only depends on β_0 and ε .

In exploratory studies which are not formally powered, dose proportionality is generally concluded if 90% confidence intervals (CI) around the slope (i.e., β_1) includes the value of 1.0.

In addition, graphs of baseline corrected C_{\max} versus Dose and AUC_{0-2h} versus Dose will be generated. The graphs will display the individual points and include the mean value as a distinct highlighted point.

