3.3. Statistical Hypotheses

There are no formal statistical hypotheses defined for this Phase IIa study. All data will be compared descriptively.

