3.4. Pharmacokinetic and Pharmacodynamic Hypotheses

There are no formal statistical hypotheses for PK and PD_{yn} for this Phase IIa study.

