17.2.2. Planned Summary Tables

The following tables are planned to be generated for the INP103-201 study (Note: Numbering is indicative only and may be updated based on CSR requirements):

| Header | Table Number | Table Title | Analysis Population | Interim Analysis | Priority |
|--------|--------------|---|---------------------|------------------|----------|
| 14 | | Tables and Figures | | | |
| 14.1 | | Demographic Data Summary and Tables | | | |
| | 14.1.1 | Subject Disposition | | | |
| | 14.1.1.1 | Study Participation and Disposition | ITT | N | 1 |
| | 14.1.2 | Demographics | | | |
| | 14.1.2.1 | Demographics | ITT | N | 2 |
| | 14.1.3 | Medications | | | |
| | 14.1.3.1 | Concomitant Medications | ITT | Y | 2 |
| | 14.1.3.2 | Rescue OFF Tx Allowed and Usual Morning anti-PD Medication | ITT | Y | 2 |
| 14.2 | | Pharmacokinetic and Efficacy Summary Table | | | |
| | 14.2.1 | Pharmacokinetic – Levodopa | | | |
| | 14.2.1.1.1 | Uncorrected Plasma Levodopa Concentrations | ITT | Y | 1 |
| | 14.2.1.1.2 | Baseline-Corrected Plasma Levodopa Concentrations | ITT | N | 2 |
| | 14.2.1.1.3 | Plasma Carbidopa Concentrations | ITT | N | 2 |
| Figure | 14.2.1.2.1 | Mean Uncorrected Plasma Levodopa Concentrations (Linear) | ITT | Y | 2 |
| Figure | 14.2.1.2.2 | Mean Baseline-Corrected Plasma Levodopa Concentrations (Linear) | ITT | N | 2 |
| Figure | 14.2.1.2.3 | Mean Plasma Carbidopa Concentrations (Linear) | ITT | N | 2 |

CONFIDENTIAL AND PROPRIETARY

| Header | Table Number | Table Title | Analysis Population | Interim Analysis | Priority |
|--------|--------------|--|---------------------|------------------|----------|
| Figure | 14.2.1.3.1 | Mean Uncorrected Plasma Levodopa Concentrations (Semi-Log) | ITT | Y | 2 |
| Figure | 14.2.1.3.2 | Mean Baseline-Corrected Plasma Levodopa Concentrations (Semi-Log) | ITT | N | 2 |
| Figure | 14.2.1.3.3 | Mean Plasma Carbidopa Concentrations (Semi-Log) | ITT | N | 2 |
| | 14.2.1.4.1 | Plasma Pharmacokinetic Parameter of Uncorrected Levodopa | PKP | Y | 2 |
| | 14.2.1.4.2 | Plasma Pharmacokinetic Parameter of Baseline-Corrected Levodopa | PKP | N | 2 |
| | 14.2.1.4.3 | Plasma Pharmacokinetic Parameter of Carbidopa | PKP | N | 2 |
| | 14.2.1.5 | Dose Proportionality of Baseline-Corrected Levodopa | PKP | N | 2 |
| Figure | 14.2.1.6 | Relationship of Baseline-Corrected Levodopa Pharmacokinetic Parameters with Dose | PKP | N | 2 |
| | 14.2.2 | Efficacy summary table | | | |

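### SAP 13.1.4 reads a 90% confidence interval that includes a slope of 1.0 as dose proportionality, so when the true slope is not 1, imprecise data make that conclusion more likely

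*SAP*

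**What the plan says.** SAP 13.1.4 regresses the log of baseline-corrected Cmax and AUC0-2h on log dose. On estimation it says: "The power model will be used to estimate the slope parameter and the 90% confidence intervals for the slope". It also asks for plots of each parameter against dose: "The graphs will display the individual points and include the mean value as a distinct highlighted point". SAP 13.1.3 requires, by dose group, the "geometric mean, coefficient of variation as a percent (CV%) and geometric CV".

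The interpretation is one sentence: "In exploratory studies which are not formally powered, dose proportionality is generally concluded if 90% confidence intervals (CI) around the slope" (the parameter β1) "includes the value of 1.0". The section sets no equivalence limits, no maximum interval width and no inconclusive outcome. Protocol 12.4 has no rule on dose proportionality, so this is the only one in either document.

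Elsewhere the SAP is descriptive. Section 3.3 says "All data will be compared descriptively" and section 3.4 says "There are no formal statistical hypotheses for PK". The output, Table 14.2.1.5 "Dose Proportionality of Baseline-Corrected Levodopa", is listed in SAP 17.2.2 as Priority 2 and is not part of the interim analysis.

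**The concern.** A 90% interval that includes 1 means only that a slope of 1 was not rejected at the two-sided 10% level. It does not show that the slope is close to 1. If the true slope is not 1, a wider interval is more likely to include 1, so poorer data raise the chance of a proportional verdict. That the study is exploratory and unpowered is a reason to report an estimate with its uncertainty. It does not justify a positive conclusion drawn from a non-rejection.

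At stake is a sentence in the report on how levodopa exposure rises from 35 to 140 mg. Such a sentence can be carried into later work without its interval. Nothing else depends on it: the primary safety endpoints and the Safety Monitoring Committee's escalation decisions are unaffected.

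**Working it through.** The SAP gives no power or precision figure for this analysis, so there is no stated figure to reproduce. The question is how often the rule returns a proportional verdict.

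**Inputs**
- Doses 35, 70 and 140 mg with 6 active subjects each (SAP 4.2): n = 18, residual df = 16.
- 90% interval (SAP 13.1.4): t(0.95, 16) = 1.746.
- Between-subject CV: not given for humans in either document. Assumed 20, 30, 50 and 70%.
- True slopes of 0.7 and 0.5: chosen for illustration. Over the 4-fold dose range they mean exposure ratios of 4^0.7 = 2.6 and 4^0.5 = 2.0, against 4.0 under proportionality.

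**Formulas**
- The log doses are equally spaced by ln 2, so Sxx = 6(ln 2)² + 0 + 6(ln 2)² = 12 × 0.4805 = 5.765, and √Sxx = 2.401.
- Residual SD on the log scale: σ = √ln(1 + CV²).
- SE(slope) = σ/2.401.
- P(interval includes 1) = P(|T| < 1.746), where T is noncentral t with 16 df and noncentrality (true slope − 1)/SE.

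Example, CV 50% and slope 0.7: σ = √ln 1.25 = 0.472; SE = 0.472/2.401 = 0.197; noncentrality = −0.3/0.197 = −1.52; probability 0.572.

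| CV | 20% | 30% | 50% | 70% |
|---|---|---|---|---|
| Called proportional, true slope 0.7 | 0.033 | 0.241 | 0.572 | 0.707 |
| Called proportional, true slope 0.5 | 0.000 | 0.012 | 0.216 | 0.430 |
| Called proportional, true slope 1 | 0.90 | 0.90 | 0.90 | 0.90 |
| Expected half-width of slope interval | 0.142 | 0.210 | 0.338 | 0.452 |
| Interval for 35 to 140 mg exposure ratio if estimated slope is 1 | 3.3–4.9 | 3.0–5.4 | 2.5–6.4 | 2.1–7.5 |

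The last row is 4 divided and multiplied by 4^half-width, that is by 1.22, 1.34, 1.60 and 1.87. Simulation of 200,000 trials per setting agrees with the probabilities for slopes 0.7 and 0.5 (0.034/0.240/0.571/0.704 and 0.000/0.012/0.217/0.429).

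**Variability figures in the documents.** Protocol 1.2.1 gives monkey values with an unlabelled ±. Read as SDs, they give these CVs:
- AUC: 22,112/149,941 = 14.7% and 18,094/92,404 = 19.6%.
- Cmax: 198/1,608 = 12.3% and 413/1,310 = 31.5%.

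In increasing order of CV (12.3, 14.7, 19.6, 31.5%), the slope-0.7 error rates are 0.000, 0.001, 0.028 and 0.276. At slope 0.5 the highest is 0.019. Monkey values do not establish the human CV.

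**Cohort 4.** SAP 13.1.4 does not say whether Cohort 4 enters the model. It has the same levodopa dose as Cohort 2 but a different formulation and decarboxylase inhibitor. Because 70 mg is the centre of the log-dose range, adding six such subjects leaves Sxx at 5.765 and does not bias the slope. The results below come from 60,000 simulated trials per setting, at slope 0.7 and CV 20, 30 and 50%:
- With no exposure shift, the rates barely change: 0.030, 0.234 and 0.566.
- With a 1.62-fold shift (the monkey AUC ratio 149,941/92,404, used only as an illustration), the half-widths become 0.209, 0.259 and 0.368, and the rates rise to 0.146, 0.376 and 0.629.

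**The case against.** The strongest reply concerns weight. Dose proportionality is not an objective or endpoint in either document. The sentence is phrased as a general convention and does not say what this report will conclude. The slope, its interval, the individual plots and the geometric summaries are all required, so a reader can see a wide interval. The rule does not reward imprecision when the true slope is 1, because the rate is then 90% at every CV. The large error rates need CVs of 50 to 70%, which nothing in the documents supports; the monkey CVs give mostly small ones. The slopes of 0.7 and 0.5 are also choices, and the calculation assumes that all 18 active subjects are evaluable at nominal dose, whereas SAP 6.5.5 admits partial-dose subjects and requires sufficient samples.

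These points are accurate and they limit the consequence. They do not rescue the rule. It is the only guidance given to the person writing the report, and visible uncertainty in a table does not correct a wrong verdict in the text. Characterising the pharmacokinetics is a secondary objective, and this is the sponsor's first clinical study of the product (Protocol 1.2.2). A rule fixed before the human CV is known should not depend on that CV being low.

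**Conclusion.** The concern holds. The model, the 90% interval and the displays are sound; the fault is the one sentence that turns non-rejection into a conclusion. With 18 active subjects, a true slope of 0.7 would be called proportional in about 3% of trials at CV 20% and 71% at CV 70%. A true slope of 0.5 would be called proportional in about 0% and 43%. These figures rest on an assumed human CV, illustrative slopes, log-normal residuals with equal variance, and complete data at nominal doses. At low CV the practical effect is small. The reach is confined to exploratory pharmacokinetic reporting, but the rule as written is wrong and should be changed. The silence on Cohort 4 is a minor specification gap.

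**What to change.** Replace the interpretive sentence in SAP 13.1.4 with wording such as:

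> The slope and its 90% CI will be reported with the implied exposure ratio over 35 to 140 mg (4^slope) and its 90% CI. If the CI includes 1.0, the report will state that no departure from dose proportionality was detected and will not conclude proportionality. If it excludes 1.0, the report will state that a departure was detected and give its size.

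No equivalence limits are needed. If a positive proportional verdict is wanted, the whole interval should have to lie within limits set in advance. This sample could rarely meet tight ones: with illustrative slope limits of 1 ± ln 1.25/ln 4 (0.839 to 1.161) and a true slope of 1, the chance of success is about 21% at CV 20% and 1% at CV 30%.

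Add one line on Cohort 4: the model will be fitted to Cohorts 1 to 3, and Cohort 4 will be compared descriptively with Cohort 2.

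The cost is SAP wording plus one extra output, 4 raised to the slope and to its interval limits. The report loses a simple verdict. At a true slope of 1 a departure would still be reported in 10% of trials, which is why its size must be given.

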13.2. Pharmacodynamic Analyses

Refer to section 10. Efficacy Analyses.

13.3. Pharmacokinetic/Pharmacodynamic relationship

Exploratory graphical analysis of the time-matched change from baseline in MDS-UPDRS Part III score versus uncorrected plasma L-Dopa concentrations

14. PHARMACOGENETIC DATA ANALYSES

Not applicable for this study.

15. VIRAL GENOTYPING/PHENOTYPING

Not applicable for this study.

17.2. Table of Contents for Data Display Specifications

17.2.1. Planned Data Listings

The following listings are planned to be generated for the INP103-201 study (Note: Numbering is indicative only and may be updated based on CSR requirements):

| Header | Listing Number | Listing Title | Analysis Population | Interim Analysis | Priority |
|--------|----------------|--|---------------------|------------------|----------|
| 16.2 | | Subject Data Listings | | | |
| 16.2.1 | | Subject Disposition | | | |
| | 16.2.1.1 | Study Enrolment and Completion/Discontinuation | ITT | N | 1 |
| | 16.2.1.2 | Visit Dates and Study Days | ITT | N | 2 |
| 16.2.2 | | Protocol Deviations | | | |
| | 16.2.2.1 | Protocol Deviations | ITT | N | 1 |
| 16.2.3 | | Subjects Excluded from Analyses | | | |
| | 16.2.3.1 | Population Assignment and Reason for Exclusion | ITT | N | 1 |
| 16.2.4 | | Demographic and Other Baseline Data | | | |
| | 16.2.4.1 | Demographics | ITT | N | 2 |
| | 16.2.4.2 | Inclusion/Exclusion Criteria | ITT | N | 2 |
| | 16.2.4.3 | Medical History | ITT | N | 2 |
| | 16.2.4.4 | Smoking History | ITT | N | 2 |
| | 16.2.4.5 | Parkinson's Disease History | ITT | N | 2 |
| | 16.2.4.6 | Pregnancy Test | ITT | N | 2 |
| | 16.2.4.7.1 | Prior Medications | ITT | Y | 2 |

CONFIDENTIAL AND PROPRIETARY

| Header | Listing Number | Listing Title | Analysis Population | Interim Analysis | Priority |
|--------|----------------|---|---------------------|------------------|----------|
| | 16.2.4.7.2 | Concomitant Medications | ITT | Y | 2 |
| | 16.2.4.7.3 | Rescue OFF Tx Allowed | ITT | Y | 2 |
| | 16.2.4.7.4 | Usual Morning anti-PD Medication | ITT | Y | 1 |
| | 16.2.4.7.5 | Levodopa Medication | ITT | Y | 1 |
| 16.2.5 | | Compliance and/or drug concentration data | | | |
| | 16.2.5.1 | Subject Randomization | ITT | N | 1 |
| | 16.2.5.2 | Drug Administration: Benserazide | ITT | N | 2 |
| | 16.2.5.3 | Drug Administration: INP103/Placebo | ITT | N | 2 |
| | 16.2.5.4 | Drug Administration: ON medication | ITT | N | 2 |
| 16.2.6 | | Pharmacokinetic and Efficacy Data Listing | | | |
| | 16.2.6.1 | Pharmacokinetic: | | | |
| | 16.2.6.1.1.1 | Plasma Pharmacokinetic Sample Collection Time and Levodopa Concentrations | ITT | N | 1 |
| | 16.2.6.1.1.2 | Plasma Pharmacokinetic Sample Collection Time Carbidopa Concentrations | ITT | N | 2 |
| Figure | 16.2.6.1.2.1 | Individual Uncorrected Plasma Levodopa Concentrations Over Time, by Treatment Group (Linear) | ITT | N | 2 |
| Figure | 16.2.6.1.2.2 | Individual Baseline-Corrected Plasma Levodopa Concentrations Over Time, by Treatment Group (Linear) | ITT | N | 2 |
| Figure | 16.2.6.1.2.3 | Individual Plasma Carbidopa Concentrations Over Time, by Treatment Group (Linear) | ITT | N | 2 |
| Figure | 16.2.6.1.3.1 | Individual Uncorrected Plasma Levodopa Concentrations Over Time, by Treatment Group (Semi-Log) | ITT | N | 2 |

CONFIDENTIAL AND PROPRIETARY

| Header | Listing Number | Listing Title | Analysis Population | Interim Analysis | Priority |
|--------|----------------|--|---------------------|------------------|----------|
| Figure | 16.2.6.1.3.2 | Individual Baseline-Corrected Plasma Levodopa Concentrations Over Time, by Treatment Group (Semi-Log) | ITT | N | 2 |
| Figure | 16.2.6.1.3.3 | Individual Plasma Carbidopa Concentrations Over Time, by Treatment Group (Semi-Log) | ITT | N | 2 |
| | 16.2.6.1.4.1 | Plasma Pharmacokinetic Parameter of Uncorrected Levodopa | PKP | N | 1 |
| | 16.2.6.1.4.2 | Plasma Pharmacokinetic Parameter of Baseline-Corrected Levodopa | PKP | N | 2 |
| | 16.2.6.1.4.3 | Plasma Pharmacokinetic Parameter of Carbidopa | PKP | N | 2 |
| | 16.2.6.2 | Efficacy data listing | | | |
| | 16.2.6.2.1 | Movement Disorder Society Unified Parkinson's Disease Rating Scale (MDS-UPDRS) Full Score | ITT | N | 2 |
| | 16.2.6.2.2 | Movement Disorder Society Unified Parkinson's Disease Rating Scale (MDS-UPDRS) Part III Motor Score | ITT | Y | 1 |
| | 16.2.6.2.3 | Movement Disorder Society Unified Parkinson's Disease Rating Scale (MDS-UPDRS) Part III Total Motor Score | ITT | Y | 1 |
| | 16.2.6.2.4 | Movement Disorder Society Unified Parkinson's Disease Rating Scale (MDS-UPDRS) Part III Total Motor Score - Response | ITT | Y | 2 |
| | 16.2.6.2.5 | Movement Disorder Society Unified Parkinson's Disease Rating Scale (MDS-UPDRS) Part III Total Motor Score - Area Under Curve | ITT | Y | 2 |
| | 16.2.6.2.6 | Evaluation of ON/OFF status | ITT | Y | 2 |
| | 16.2.6.2.7 | Time to ON/OFF status | ITT | Y | 2 |
| 16.2.7 | | Adverse Event Listings | | | |
| | 16.2.7.1 | Adverse Events | ITT | Y | 1 |

CONFIDENTIAL AND PROPRIETARY

| Header | Listing Number | Listing Title | Analysis Population | Interim Analysis | Priority |
|--------|----------------|--|---------------------|------------------|----------|
| | 16.2.7.2 | Serious Adverse Events | ITT | Y | 1 |
| | 16.2.7.3 | Adverse Events leading to Study Discontinuation or Study Drug Withdrawal | ITT | Y | 1 |
| | 16.2.7.4 | Adverse Events Leading to Death | ITT | Y | 1 |
| 16.2.8 | | Clinical Laboratory Data | | | |
| | 16.2.8.1 | Individual Hematology Results | ITT | Y | 2 |
| | 16.2.8.2 | Individual Biochemistry Results | ITT | Y | 2 |
| | 16.2.8.3 | Individual Urinalysis Results | ITT | Y | 2 |
| | 16.2.8.4 | Individual Microscopy Results | ITT | Y | 2 |
| 16.4 | | Other Safety Data | | | |
| | 16.4.1.1 | Vital Signs | ITT | Y | 2 |
| | 16.4.1.2 | Detection of Orthostatic Hypotension | ITT | Y | 2 |
| | 16.4.2 | ECG Findings and Changes from Baseline | ITT | Y | 2 |
| | 16.4.3 | Dyskinesia Examination | ITT | Y | 2 |
| | 16.4.4 | Nasal Examination | ITT | Y | 1 |
| | 16.4.5 | Physical Examination | ITT | Y | 2 |
| | 16.4.6 | Subject Questionnaire | ITT | N | 2 |
| | 16.4.7 | Domiciled Status | ITT | N | 2 |
| | 16.4.8 | General Comments | ITT | N | 2 |

CONFIDENTIAL AND PROPRIETARY

17.2.2. Planned Summary Tables

The following tables are planned to be generated for the INP103-201 study (Note: Numbering is indicative only and may be updated based on CSR requirements):

| Header | Table Number | Table Title | Analysis Population | Interim Analysis | Priority |
|--------|--------------|---|---------------------|------------------|----------|
| 14 | | Tables and Figures | | | |
| 14.1 | | Demographic Data Summary and Tables | | | |
| | 14.1.1 | Subject Disposition | | | |
| | 14.1.1.1 | Study Participation and Disposition | ITT | N | 1 |
| | 14.1.2 | Demographics | | | |
| | 14.1.2.1 | Demographics | ITT | N | 2 |
| | 14.1.3 | Medications | | | |
| | 14.1.3.1 | Concomitant Medications | ITT | Y | 2 |
| | 14.1.3.2 | Rescue OFF Tx Allowed and Usual Morning anti-PD Medication | ITT | Y | 2 |
| 14.2 | | Pharmacokinetic and Efficacy Summary Table | | | |
| | 14.2.1 | Pharmacokinetic – Levodopa | | | |
| | 14.2.1.1.1 | Uncorrected Plasma Levodopa Concentrations | ITT | Y | 1 |
| | 14.2.1.1.2 | Baseline-Corrected Plasma Levodopa Concentrations | ITT | N | 2 |
| | 14.2.1.1.3 | Plasma Carbidopa Concentrations | ITT | N | 2 |
| Figure | 14.2.1.2.1 | Mean Uncorrected Plasma Levodopa Concentrations (Linear) | ITT | Y | 2 |
| Figure | 14.2.1.2.2 | Mean Baseline-Corrected Plasma Levodopa Concentrations (Linear) | ITT | N | 2 |
| Figure | 14.2.1.2.3 | Mean Plasma Carbidopa Concentrations (Linear) | ITT | N | 2 |

CONFIDENTIAL AND PROPRIETARY

| Header | Table Number | Table Title | Analysis Population | Interim Analysis | Priority |
|--------|--------------|--|---------------------|------------------|----------|
| Figure | 14.2.1.3.1 | Mean Uncorrected Plasma Levodopa Concentrations (Semi-Log) | ITT | Y | 2 |
| Figure | 14.2.1.3.2 | Mean Baseline-Corrected Plasma Levodopa Concentrations (Semi-Log) | ITT | N | 2 |
| Figure | 14.2.1.3.3 | Mean Plasma Carbidopa Concentrations (Semi-Log) | ITT | N | 2 |
| | 14.2.1.4.1 | Plasma Pharmacokinetic Parameter of Uncorrected Levodopa | PKP | Y | 2 |
| | 14.2.1.4.2 | Plasma Pharmacokinetic Parameter of Baseline-Corrected Levodopa | PKP | N | 2 |
| | 14.2.1.4.3 | Plasma Pharmacokinetic Parameter of Carbidopa | PKP | N | 2 |
| | 14.2.1.5 | Dose Proportionality of Baseline-Corrected Levodopa | PKP | N | 2 |
| Figure | 14.2.1.6 | Relationship of Baseline-Corrected Levodopa Pharmacokinetic Parameters with Dose | PKP | N | 2 |
| | 14.2.2 | Efficacy summary table | | | |
| | 14.2.2.1 | Summary of Movement Disorder Society Unified Parkinson's Disease Rating Scale (MDS-UPDRS) Part III Score | ITT | Y | 1 |
| | 14.2.2.2 | MMRM of Movement Disorder Society Unified Parkinson's Disease Rating Scale (MDS-UPDRS) Part III Score | ITT | N | 2 |
| Figure | 14.2.2.3 | Individual Change from Baseline in Movement Disorder Society Unified Parkinson's Disease Rating Scale (MDS-UPDRS) Part III Score | ITT | N | 2 |
| | 14.2.2.4 | Summary of Cumulative Response | ITT | Y | 2 |
| | 14.2.2.5 | Summary of Time-to-Response | ITT | Y | 2 |
| | 14.2.2.6 | Duration of Response | ITT | N | 2 |
| Figure | 14.2.2.7 | Kaplan-Meier Plot for Time-to-Response | ITT | N | 2 |
| | 14.2.2.8 | Summary of AUC of change in Movement Disorder Society Unified Parkinson's Disease Rating Scale (MDS-UPDRS) Part III Score | ITT | N | 2 |

CONFIDENTIAL AND PROPRIETARY

| Header | Table Number | Table Title | Analysis Population | Interim Analysis | Priority |
|--------|--------------|--|---------------------|------------------|----------|
| | 14.2.2.9 | ANCOVA of AUC of change in Movement Disorder Society Unified Parkinson's Disease Rating Scale (MDS-UPDRS) Part III Score | ITT | N | 2 |
| | 14.2.2.10 | Summary of the Maximum Response | ITT | Y | 2 |
| | 14.2.2.11 | ANCOVA of The Maximum Response | ITT | N | 2 |
| | 14.2.2.12 | Summary of Time-to-ON | ITT | Y | 2 |
| Figure | 14.2.2.13 | Kaplan-Meier estimator for Time-to-ON status | ITT | N | 2 |
| | 14.2.3 | Pharmacokinetic versus Pharmacodynamic Relationship | | | |
| Figure | 14.2.3.1 | Time-matched Change from baseline in MDS-UPDRS Part III score versus uncorrected plasma L-Dopa concentrations | ITT | N | 2 |
| 14.3 | | Safety Data Summary Tables | | | |
| | 14.3.1 | Adverse Events | | | |
| | 14.3.1.1 | Overall Summary of Treatment Emergent Adverse Events | Safety | Y | 1 |
| | 14.3.1.2 | Adverse Events onset within Benserazide Period | Benserazide Safety | N | 2 |
| | 14.3.1.3 | Treatment Emergent Adverse Events | Safety | Y | 1 |
| | 14.3.1.4 | Treatment Emergent Adverse Events by Severity | Safety | N | 2 |
| | 14.3.1.5 | Treatment-Related Treatment Emergent Adverse Events | Safety | N | 2 |
| | 14.3.1.6 | Serious Treatment Emergent Adverse Events | Safety | N | 1 |
| | 14.3.2 | Listings of Deaths, Other Serious and Significant Adverse Events | Not Applicable | | |

CONFIDENTIAL AND PROPRIETARY

| Header | Table Number | Table Title | Analysis Population | Interim Analysis | Priority |
|--------|--------------|--|---------------------|------------------|----------|
| | 14.3.3 | Narratives of Deaths, Other Serious and Certain Other Significant Adverse Events | Not Applicable | | |
| | 14.3.4 | Clinical Laboratory Data | | | |
| | 14.3.4.1 | Hematology Results and Change from Baseline | Safety | N | 2 |
| | 14.3.4.2 | Biochemistry Results and Change from Baseline | Safety | N | 2 |
| | 14.3.4.3 | Urinalysis Results | Safety | N | 2 |
| | 14.3.5 | Vital Signs | | | |
| | 14.3.5.1 | Vital Signs Values and Change from Baseline | Safety | N | 2 |
| | 14.3.5.2 | Detection of Orthostatic hypotension | Safety | N | 2 |
| | 14.3.6 | ECG Findings | | | |
| | 14.3.6.1 | ECG Values and Change from Baseline | Safety | N | 2 |
| | 14.3.6.2 | ECG Clinical Assessment Results | Safety | N | 2 |
| | 14.3.6.3 | ECG Clinical Assessment Results: Criteria of QTc value | Safety | N | 2 |
| | 14.3.7 | Other Safety Result | | | |
| | 14.3.7.1 | Summary of Dyskinesia Examination | Safety | N | 2 |
| | 14.3.7.2 | Summary of Nasal Examination | Safety | N | 2 |
| | 14.3.7.3 | Summary of Abnormal Physical Examination | Safety | N | 2 |

CONFIDENTIAL AND PROPRIETARY
